10.14 Edinburgh Postnatal Depression Scale

Tables summarizing results from the Edinburgh Postnatal Depression Scale will be prepared. These summaries will be by visit, by arm and overall for each of the three cohorts, and by visit, by arm and overall for the three cohorts combined. These will be summarized for visits where the questionnaire was expected to be administered.

Expected visits for the Edinburgh Postnatal Depression Scale are the following:

- Enrollment visit (visit 2)
- 4-week visit corresponding to, or immediately following, the 30th week of gestation (only for Cohort 3; this is visit 6 if the gestational age at enrollment was 26-29 weeks, visit 10 if the GA was 22-25 weeks, visit 14 if the GA was 18-21 weeks, visit 18 if the GA was 14-17 weeks, or visit 22 if the GA was 12-13 weeks)
- 6-week PPO visit (visit 103)

These tables will use data collected on the Edinburgh Postnatal Depression Score CRF and will include:

- Number and percentage of participants with an assessment performed (“Was this assessment performed?” was “Yes”), with the denominator being the number of participants in the ITT Analysis Set who completed the visit.
- Number and percentage of participants with each response to the 10 items on the questionnaire (“I have been able to laugh and see the funny side of things”, “I have looked forward with enjoyment to things”, “I have blamed myself unnecessarily when things went wrong”, “I have been anxious or worried for no good reason”, “I have felt scared or panicky for no very good reason”, “Things have been getting on top of me”, “I have been so unhappy that I have had difficulty sleeping”, “I have felt sad or miserable”, “I have been so unhappy that I have been crying”, “The thought of harming myself has occurred to me”), with the denominator being the number of participants in the ITT Analysis Set with an assessment performed.
- Number and percentage of participants who were subsequently referred for further evaluation and/or management (“Following completion of this questionnaire, was the mother subsequently referred for further evaluation and/or management”), with the denominator being the number of participants in the ITT Analysis Set with an assessment performed.
- Summary of the EPDS Score as a continuous variable.

10.15 Infant Demographics

Tables summarizing infant sex at birth will be prepared and will be by arm and overall for each of the three cohorts, and by arm and overall for the three cohorts combined. These will be summarized using the “sex at birth” item on the Infant Demographics CRF.

10.16 Social Benefits

Tables summarizing social benefits will be prepared and will be by arm and overall for each of the three cohorts, and by arm and overall for the three cohorts combined. These summaries will include responses from the Social Benefits CRF collected at the 6-week PPO visit (visit 103), including interim 6-week PPO visits for participants who did not have the Social Benefits CRF collected at their scheduled 6-week PPO visit.

These tables will include:

- Numbers and percentages of participants with each possible response to items under “From your perspective, what are all the benefits of participating in this study?” (i.e., from “The financial reimbursement”, “Free health care from the study”,..., “To help my relationship with my partner and/or family”, and “Other”), with the denominators being the number of participants in the ITT Analysis Set.
- Number and percentage of participants with each response to “What is the most important benefit or reason for your participation in this study?”, with the denominator being the number of participants in the ITT Analysis Set.

10.17 Social Impacts

Tables summarizing social impacts will be prepared and will be by arm and overall for each of the three cohorts, and by arm and overall for the three cohorts combined. These tables will include:

- Number and percentage of participants who reported a social impact during the study (any Social Impact Y/N CRF with a “Has the participant reported a social impact during the study?” of “Yes”), with the denominator being the number of participants in the ITT Analysis Set.
- Number and percentage of participants with each type of social impact (“Social impact type” from the Social Impact Log CRF) and the total number of each type of impact. The denominator will be the number of participants who reported a social impact.
- Number and percentage of participants who reported an impact involving physical harm (“Did this involve physical harm to the participant?”) and the total number of impacts involving physical harm. The denominator will be the number of participants who reported a social impact.
- Number and percentage of participants who reported an impact involving harm to children (“Did this involve physical or other harm to participant’s child(ren)?”) and the total number of impacts involving harm to children. The denominator will be the number of participants who reported a social impact.
- The total number of impacts with each level of impact (“What impact did this situation have on the participant’s quality of life?”, responses of “minimal disturbance”, “moderate disturbance; no significant impact”, and “major disturbance with significant impact”).
- The total number of impacts with each current status (“Current status”, responses of “unresolved”, “unresolved at end of study”, “unable to resolve; no further action taken”, “resolved”).

11. CHANGE HISTORY

Version		Affected Section(s)	Activity Description
Number	Effective Date		
1.0	Date of last signature	All	New document

12. APPENDIX I Mother Expected Visits from Week 5 until Pregnancy Outcome

Table 3: Cohort 1 Mother Expected Visits from Week 5 until Pregnancy Outcome

GA (wks) at Enrollment	Week 5 (phone contact)
37	
36	Visit (GA 41)

Cells shaded blue represent expected phone contact visits. The parenthetical "GA x" displays the gestational age in weeks of the participant at that visit. Visits in this table are only considered expected up until the participant's pregnancy outcome.

Note that the 37 weeks gestational age at enrollment group did not have any expected visits between Visit 6 – Week 4 and their pregnancy outcome.

Table 4: Cohort 2 Mother Expected Visits from Week 5 until Pregnancy Outcome

GA (wks) at Enrollment	Week 5 (phone contact)	Week 6 (in-person)	Week 7 (phone contact)	Week 8 (in-person)	Week 9 (phone contact)	Week 10 (in-person)	Week 11 (phone contact)
35	Visit 7 (GA 40)	Visit 8 (GA 41)					
34	Visit 7 (GA 39)	Visit 8 (GA 40)	Visit 9 (GA 41)				
33	Visit 7 (GA 38)	Visit 8 (GA 39)	Visit 9 (GA 40)	Visit 10 (GA 41)			
32	Visit 7 (GA 37)	Visit 8 (GA 38)	Visit 9 (GA 39)	Visit 10 (GA 40)	Visit 11 (GA 41)		
31	Visit 7 (GA 36)	Visit 8 (GA 37)	Visit 9 (GA 38)	Visit 10 (GA 39)	Visit 11 (GA 40)	Visit 12 (GA 41)	
30		Visit 8 (GA 36)	Visit 9 (GA 37)	Visit 10 (GA 38)	Visit 11 (GA 39)	Visit 12 (GA 40)	Visit 13 (GA 41)

Cells shaded blue represent expected phone contact visits. Cells shaded yellow represent expected in-person visits. The parenthetical "GA x" displays the gestational age in weeks of the participant at that visit. Visits in this table are only considered expected up until the participant's pregnancy outcome.

Table 5: Cohort 3 GA 24-29 weeks Mother Expected Visits from Week 5 until Pregnancy Outcome

Cells shaded blue represent expected phone contact visits. Cells shaded yellow represent expected in-person visits. The parenthetical "GA x" displays the gestational age in weeks of the participant at that visit. Visits in this table are only considered expected up until the participant's pregnancy outcome.

GA (wks) at Enroll	Week 7 (phone contact)	Week 8 (in-person)	Week 9 (phone contact)	Week 10 (in-person)	Week 11 (phone contact)	Week 12 (in-person)	Week 13 (phone contact)	Week 14 (in-person)	Week 15 (phone contact)	Week 16 (in-person)	Week 17 (phone contact)
29	Visit 9 (GA 36)	Visit 10 (GA 37)	Visit 11 (GA 38)	Visit 12 (GA 39)	Visit 13 (GA 40)	Visit 14 (GA 41)					
28		Visit 10 (GA 36)	Visit 11 (GA 37)	Visit 12 (GA 38)	Visit 13 (GA 39)	Visit 14 (GA 40)	Visit 15 (GA 41)				
27		Visit 10 (GA 35)	Visit 11 (GA 36)	Visit 12 (GA 37)	Visit 13 (GA 38)	Visit 14 (GA 39)	Visit 15 (GA 40)	Visit 16 (GA 41)			
26		Visit 10 (GA 34)		Visit 12 (GA 36)	Visit 13 (GA 37)	Visit 14 (GA 38)	Visit 15 (GA 39)	Visit 16 (GA 40)	Visit 17 (GA 41)		
25		Visit 10 (GA 33)			Visit 13 (GA 36)	Visit 14 (GA 37)	Visit 15 (GA 38)	Visit 16 (GA 39)	Visit 17 (GA 40)	Visit 18 (GA 41)	
24		Visit 10 (GA 32)				Visit 14 (GA 36)	Visit 15 (GA 37)	Visit 16 (GA 38)	Visit 17 (GA 39)	Visit 18 (GA 40)	Visit 19 (GA 41)

Note that these gestational ages at enrollment groups did not have any expected visits after Visit 6 and prior to Visit 9 and these visits are omitted from Table 5.

Table 6: Cohort 3 GA 18-23 weeks Mother Expected Visits from Week 5 until Pregnancy Outcome

GA (wks) at Enroll	Wk 8	Wk 12	Wk 13	Wk 14	Wk 15	Wk 16	Wk 17	Wk 18	Wk 19	Wk 20	Wk 21	Wk 22	Wk 23
23	V10 (GA 31)	V14 (GA 35)	V15 (GA 36)	V16 (GA 37)	V17 (GA 38)	V18 (GA 39)	V19 (GA 40)	V20 (GA 41)					
22	V10 (GA 30)	V14 (GA 34)		V16 (GA 36)	V17 (GA 37)	V18 (GA 38)	V19 (GA 39)	V20 (GA 40)	V21 (GA 41)				
21	V10 (GA 29)				V17 (GA 36)	V18 (GA 37)	V19 (GA 38)	V20 (GA 39)	V21 (GA 40)	V22 (GA 41)			
20	V10 (GA 28)	V14 (GA 32)				V18 (GA 36)	V19 (GA 37)	V20 (GA 38)	V21 (GA 39)	V22 (GA 40)	V23 (GA 41)		
19	V10 (GA 27)	V14 (GA 31)				V18 (GA 35)	V19 (GA 36)	V20 (GA 37)	V21 (GA 38)	V22 (GA 39)	V23 (GA 40)	V24 (GA 41)	
18	V10 (GA 26)	V14 (GA 30)				V18 (GA 34)		V20 (GA 36)	V21 (GA 37)	V22 (GA 38)	V23 (GA 39)	V24 (GA 40)	V25 (GA 41)

Cells shaded blue represent expected phone contact visits. Cells shaded yellow represent expected in-person visits. The parenthetical "GA x" displays the gestational age in weeks of the participant at that visit. Visits in this table are only considered expected up until the participant's pregnancy outcome.

Note that these gestational age at enrollment groups did not have any expected visits after Visit 6 and prior to Visit 10, and after Visit 10 and prior to Visit 14, and these visits are omitted from Table 6.

Table 7: Cohort 3 GA 12-17 weeks Mother Expected Visits from Week 5 until Pregnancy Outcome

GA (wks) at Enroll	Wk 8	Wk 12	Wk 16	Wk 19	Wk 20	Wk 21	Wk 22	Wk 23	Wk 24	Wk 25	Wk 26	Wk 27	Wk 28	Wk 29
17	V10 (GA 25) V14 (GA 29)	V14 (GA 33)	V18 (GA 33)	V21 (GA 36)	V22 (GA 37)	V23 (GA 38)	V24 (GA 39)	V25 (GA 40)	V26 (GA 41)					
16	V10 (GA 24) V14 (GA 28)	V14 (GA 32)		V22 (GA 36)	V23 (GA 37)	V24 (GA 38)	V25 (GA 39)	V26 (GA 40)	V27 (GA 41)					
15	V10 (GA 23) V14 (GA 27)	V14 (GA 31)		V22 (GA 35)	V23 (GA 36)	V24 (GA 37)	V25 (GA 38)	V26 (GA 39)	V27 (GA 40)	V28 (GA 41)				
14	V10 (GA 22) V14 (GA 26)	V14 (GA 30)		V22 (GA 34)		V24 (GA 36)	V25 (GA 37)	V26 (GA 38)	V27 (GA 39)	V28 (GA 40)	V29 (GA 41)			
13	V10 (GA 21) V14 (GA 25)	V14 (GA 29)		V22 (GA 33)			V25 (GA 36)	V26 (GA 37)	V27 (GA 38)	V28 (GA 39)	V29 (GA 40)	V30 (GA 41)		
12	V10 (GA 20) V14 (GA 24)	V14 (GA 28)		V22 (GA 32)				V26 (GA 36)	V27 (GA 37)	V28 (GA 38)	V29 (GA 39)	V30 (GA 40)	V31 (GA 41)	

Cells shaded blue represent expected phone contact visits. Cells shaded yellow represent expected in-person visits. The parenthetical "GA x" displays the gestational age in weeks of the participant at that visit. Visits in this table are only considered expected up until the participant's pregnancy outcome.

Note that these gestational ages at enrollment groups did not have any expected visits after Visit 6 and prior to Visit 10, after Visit 10 and prior to Visit 14, after Visit 14 and prior to Visit 18, and after V18 and prior to Visit 21, and these visits are omitted from Table 7.

13. APPENDIX II Visit Timing Requirements

Table 8: Visit Timing Requirements for Mothers in Cohort 1

Visit	Target Day	Window Opens	Window Closes
Visit 1 - Screening	N/A	N/A	
Visit 2 - Day 0 Enrollment	0	Up to 35 days after screening informed consent date	
Visit 3 - Week 1 Phone Contact	7	6 days prior to target	2 days after target
Visit 4 - Week 2 Bi-weekly Visit	14	4 days prior to target	4 days after target
Visit 5 - Week 3 Phone Contact	21	2 days prior to target	2 days after target
Visit 6 - Week 4 Bi-weekly Visit	28	4 days prior to target	4 days after target
Visit 7 - Week 5 Phone Contact (women who enroll at 36 weeks GA only)	35	2 days prior to target	2 days after target
PPO Visit	as soon after the PO as possible	Pregnancy Outcome	14 days after target
1-Week PPO Phone Contact*	7 days after PO	6 days prior to target	7 days after target
6-Week PPO Visit/SEV	42 days after PO	13 days prior to target	13 days after target

*The 1-Week PPO Phone Contact may be skipped if the PPO Visit occurs within the visit window for this phone contact

Table 9: Visit Timing Requirements for Mothers in Cohort 2

Visit	Target Day	Window Opens	Window Closes
Visit 1 - Screening	N/A		N/A
Visit 2 - Day 0 Enrollment	0	Up to 35 days after screening informed consent date	
Visit 3 - Week 1 Phone Contact	7	6 days prior to target	2 days after target
Visit 4 - Week 2 2w Visit	14	4 days prior to target	4 days after target
Visit 5 - Week 3 Phone Contact	21	2 days prior to target	2 days after target
Visit 6 - Week 4 4w Visit	28	4 days prior to target	4 days after target
Visit 7 - Week 5 Phone Contact	35	2 days prior to target	2 days after target
Visit 8 - Week 6 Bi-weekly Visit	42	4 days prior to target	4 days after target
Visit 9 - Week 7 Phone Contact	49	2 days prior to target	2 days after target
Visit 10 - Week 8 Bi-weekly Visit	56	4 days prior to target	4 days after target
Visit 11 - Week 9 Phone Contact	63	2 days prior to target	2 days after target
Visit 12 - Week 10 Bi-weekly Visit	70	4 days prior to target	4 days after target
Visit 13 - Week 11 Phone Contact	77	2 days prior to target	2 days after target
Visit 101 - PPO Visit	as soon after the PO as possible	Pregnancy Outcome	14 days after target
Visit 102 - 1-Week PPO Phone Contact*	7 days after PO	7 days prior to target	7 days after target
Visit 103 - 6-Week PPO Visit/SEV	42 days after PO	13 days prior to target	13 days after target

*The 1-Week PPO Phone Contact may be skipped if the PPO Visit occurs within the visit window for this phone contact

Table 10: Visit Timing Requirements for Mothers in Cohort 3

Visit	Target Day	Window Opens	Window Closes
Visit 1 - Screening	N/A	N/A	
Visit 2 - Day 0 Enrollment	0	Up to 35 days after screening informed consent date	
Visit 3 - Week 1 Phone Contact	7	6 days prior to target	2 days after target
Visit 4 - Week 2 2w Visit	14	4 days prior to target	4 days after target
Visit 5 - Week 3 Phone Contact	21	2 days prior to target	2 days after target
Visit 6 - Week 4 4w Visit	28	4 days prior to target	4 days after target
Visit 7	N/A	N/A	
Visit 8	N/A	N/A	
Visit 9 - Week 7 Phone Contact	49	2 days prior to target	2 days after target
Visit 10 - Week 8 Bi-weekly Visit (participants enrolled at 29 weeks gestation)	56	4 days prior to target	4 days after target
Visit 10 - Week 8 4w Visit (participants enrolled at 12-28 weeks gestation)	56	4 days prior to target	4 days after target
Visit 11 - Week 9 Phone Contact	63	2 days prior to target	2 days after target
Visit 12 - Week 10 Bi-weekly Visit	70	4 days prior to target	4 days after target
Visit 13 - Week 11 Phone Contact	77	2 days prior to target	2 days after target
Visit 14 - Week 12 Bi-weekly Visit (participants enrolled at 25-29 weeks gestation)	84	4 days prior to target	4 days after target
Visit 14 - Week 12 4w Visit (participants enrolled at 12-24 weeks gestation)	84	4 days prior to target	4 days after target
Visit 15 - Week 13 Phone Contact	91	2 days prior to target	2 days after target
Visit 16 - Week 14 Bi-weekly Visit	98	4 days prior to target	4 days after target

Visit 17 - Week 15 Phone Contact	105	2 days prior to target	2 days after target
Visit 18 - Week 16 Bi-weekly Visit (participants enrolled at 21-25 weeks gestation)	112	4 days prior to target	4 days after target
Visit 18 - Week 16 4w Visit (participants enrolled at 12-20 weeks gestation)	112	4 days prior to target	4 days after target
Visit 19 - Week 17 Phone Contact	119	2 days prior to target	2 days after target
Visit 20 - Week 18 Bi-weekly Visit	126	4 days prior to target	4 days after target
Visit 21 - Week 19 Phone Contact	133	2 days prior to target	2 days after target
Visit 22 - Week 20 Bi-weekly Visit (participants enrolled at 17-21 weeks gestation)	140	4 days prior to target	4 days after target
Visit 22 - Week 20 4w Visit (participants enrolled at 12-16 weeks gestation)	140	4 days prior to target	4 days after target
Visit 23 - Week 21 Phone Contact	147	2 days prior to target	2 days after target
Visit 24 - Week 22 Bi-weekly Visit	154	4 days prior to target	4 days after target
Visit 25 - Week 23 Phone Contact	161	2 days prior to target	2 days after target
Visit 26 - Week 24 Bi-weekly Visit (participants enrolled at 13-17 weeks gestation)	168	4 days prior to target	4 days after target
Visit 26 - Week 24 4w Visit (participants enrolled at 12 weeks gestation)	168	4 days prior to target	4 days after target
Visit 27 - Week 25 Phone Contact	175	2 days prior to target	2 days after target
Visit 28 - Week 26 Bi-weekly Visit	182	4 days prior to target	4 days after target
Visit 29 - Week 27 Phone Contact	189	2 days prior to target	2 days after target

Visit 30 - Week 28 Bi-weekly Visit	196	4 days prior to target	4 days after target
Visit 31 - Week 29 Phone Contact	203	2 days prior to target	2 days after target
Visit 101 - PPO Visit	as soon after the PO as possible	Pregnancy Outcome	14 days after target
Visit 102 - 1-Week PPO Phone Contact*	7 days after PO	7 days prior to target	7 days after target
Visit 103 - 6-Week PPO Visit/SEV	42 days after PO	13 days prior to target	13 days after target

*The 1-Week PPO Phone Contact may be skipped if the PPO Visit occurs within the visit window for this phone contact

Table 11: Visit Timing Requirements for Infants

Visit	Target Day	Window Opens	Window Closes
V201 - PPO Visit	as soon after the PO as possible	Pregnancy Outcome	14 days after target
V202 - 1-Week PPO Phone Contact	7 days after PO	6 days prior to target	7 days after target
V203 - 6-Week PPO Visit	42 days after PO	13 days prior to target	13 days after target
V204 - 6-Month PPO Visit	183 days after PO	28 days prior to target	28 days after target
V205 - 12-Month PPO Visit	365 days after PO	28 days prior to target	28 days after target

*The 1-Week PPO Phone Contact may be skipped if the PPO Visit occurs within the visit window for this phone contact

14. APPENDIX III Residual Drug Levels Calculation

The DPV release rate per 28 days of use is calculated as:

$$rate = \frac{(conc_m - conc_r)}{days} \times 28$$

With $conc_m$ being the amount of residual drug in the manufacturer lot, $conc_r$ being the amount of residual drug in the returned ring, and $days$ being the number of days the participant should have been using the ring.

An individual ring is identified in the lab residual DPV data using the `guspec` identifier, with each individual ring having its own unique identifier. Some rings were tested multiple times and will have multiple observations with the same `guspec` value. Observations with censor values of "(A)X", "(A) X", "(B)X", "(B) X", "(B)Z", "(B) Z", or "Z" should not be analyzed. The amount of residual dapivirine in the ring ($conc_r$ above) is indicated by the value of `conc`.

Rings from the lab residual DPV data are linked to the clinical data through the Ring Insertion and Removal CRF, using the participant ID (`ptid`) and specimen collection date (`spcdt`) from the lab data and participant ID and the “Date ring returned” from the CRF data. For participants with multiple rings collected on the same date (i.e., two observations with same `ptid` and `spcdt` and different `guspec`), one ring needs to be assigned to correspond to “ring #1” in the Ring Return section of the CRF, and one to “ring #2”. In this case, the lab observation with the smaller value of `recnum` will be linked to the earlier ring return date on the CRF, and the larger value of `recnum` will be linked to the later ring return date.

The number of days (*days* in the above equation) is calculated by taking the specimen collection date – “date returned ring #1 was provided” + 1 day (or “date returned ring #2 was provided”), unless the specimen collection date is after the participant’s pregnancy outcome date, in which the duration is calculated as the pregnancy outcome date – “date returned ring #1 was provided” + 1 day.

Ring lot number is determined by linking the “date returned ring #1/#2 was provided” to the Pharmacy Dispensation CRF “date study product dispensed” and taking the “vaginal ring #1 lot number” or “vaginal ring #2 lot number”, as appropriate. That lot number is linked to the manufacturer record of the concentration for that lot ($conc_m$ above).

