Within Cohorts 1 and 2, participants will be randomized to the above study products in a 2:1 ratio (VR:tablet). Cohort 3 participants will be randomized to the above study products in a 4:1 ratio (200 VR:50 tablet). Participants randomized to the DPV VR will use one VR continuously for approximately one month, replacing the VR each month. Participants using Truvada tablet will take one tablet orally per day. Participants will use their assigned study product until their pregnancy outcome but no later than 41 6/7 weeks of gestation.

Figure 1: Study Visit Schedule – Cohort 2

Cohort 2	Screening
Enrollment Window	Enrollment
30 0/7 weeks of gestation – 35 6/7 weeks of gestation	1-week (phone, home or clinic as needed per local standard of care)
	2-week
	3-week (phone, home or clinic as needed per local standard of care)
	4-week
	Every odd-numbered week after 36th week of gestation (e.g., follow-up weeks 5, 7, 9) until pregnancy outcome (phone, home or clinic as needed per local standard of care)
	Every even-numbered week including and after 36th week of gestation (e.g., follow-up weeks 6, 8, 10) until pregnancy outcome
Infants enroll →	Post-pregnancy outcome visit (delivery hospital/facility or clinic)
	1-week post-pregnancy outcome (phone, home or clinic as needed per local standard of care)
Mothers exit →	Approximately 6 weeks post-pregnancy outcome
	Approximately 6 months post-delivery
	Approximately 12 months post-delivery

The primary objective of the IRP is to monitor the safety of the products being evaluated and make recommendations about the continuation, modification, or termination of either or both arms of the study in the next gestational age cohort.

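### Appendix III counts overlapping days twice when two rings worn in turn are returned on one date, so it understates the release rate of one or both rings

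*SAP*

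**What the plan says.** SAP Section 14 (Appendix III) introduces the rate with "The DPV release rate per 28 days of use is calculated as" the drug lost from the ring divided by days, times 28. It defines days as "being the number of days the participant should have been using the ring".

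The operating rule at the end of the appendix differs. The number of days "is calculated by taking the specimen collection date" and subtracting the date on which ring #1 (or ring #2) was provided, plus 1. The one exception is introduced by "unless the specimen collection date is after the participant’s pregnancy outcome date"; the period then ends at the outcome date, and that branch names only ring #1's provision date.

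The appendix foresees two rings coming back together. It has a rule that begins "For participants with multiple rings collected on the same date", under which the laboratory record with the smaller recnum "will be linked to the earlier ring return date on the CRF" and the larger recnum goes to the later one. It also foresees two rings at one dispensing, since the lot look-up uses "vaginal ring #2 lot number" as the alternative to the ring #1 lot.

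Planned use is in Section 2.1: "Participants randomized to the DPV VR will use one VR continuously for approximately one month, replacing the VR each month". Section 9.3 classes the rate as Red (up to 0.9 mg/month), Yellow (above 0.9 and up to 4.0) or Green (above 4.0).

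**The concern.** The definition and the operating rule agree for a single ring handed out at one visit, worn, and returned at the next. They part when two rings worn in turn share a return date. Nothing ends ring #1's period when ring #2 is started, and nothing delays ring #2's period until ring #1 is taken out. The same calendar days are then charged to both rings. The denominator is too large for at least one of them, and a woman who wore a ring throughout looks less adherent than she was.

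The linking rule adds a second problem. Rings are matched to the clinical record on participant and return date, and the recnum rule applies only when two rings share that date. Such rings have no earlier and later return date, so the rule cannot decide which provision date, or which lot, belongs to which ring.

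At stake are the residual-drug summaries (mean, SD, median, IQR, range) and the Red/Yellow/Green counts, which serve a listed secondary adherence endpoint.

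**Working it through.** The SAP gives no worked rate to reproduce, so the check evaluates its formula directly.

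**Inputs.** From Appendix III: rate = loss / days × 28, and days = return date − date provided + 1. From Section 9.3: the cuts at 0.9 and 4.0 mg/month. From Section 2.1: one ring at a time, changed about monthly. Assumed: the drug lost in 28 days of full wear, which the SAP does not state and which is varied below.

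**Reference case.** One ring provided on Day 0 and returned on Day 28: days = 28 − 0 + 1 = 29, and the rate is 28/29 = 0.966 of the loss. Green needs a loss above 4.0 × 29/28 = 4.14 mg.

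**Case A.** Both rings provided on Day 0, worn 28 days each in turn, both returned on Day 56. Days = 57 and 57, so 114 ring-days are charged for 57 calendar days. Each rate is 28/57 = 0.491 of the 28-day rate.

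**Case B.** Ring #1 provided on Day 0, ring #2 on Day 28, both returned on Day 56. Days = 57 and 29, which is 86 ring-days. Ring #1 is at 0.491; ring #2 is at 0.966, the same as any single ring.

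**Category of a ring charged 57 days.** Green needs a loss above 4.0 × 57/28 = 8.14 mg. Red needs a loss of at most 0.9 × 57/28 = 1.83 mg. A fully worn ring therefore moves from Green to Yellow for losses above 4.14 and up to 8.14 mg.

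| Loss in 28 days (mg, assumed) | Charged 29 days | Charged 57 days | Pooled, both rings (2 × loss / 57 × 28) |
|---|---|---|---|
| 4.2 | 4.06 Green | 2.06 Yellow | 4.13 Green |
| 5 | 4.83 Green | 2.46 Yellow | 4.91 Green |
| 6 | 5.79 Green | 2.95 Yellow | 5.89 Green |
| 8 | 7.72 Green | 3.93 Yellow | 7.86 Green |
| 9 | 8.69 Green | 4.42 Green | 8.84 Green |

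**A swapped link.** Assume 4.5 mg per 28 days. Ring A is worn on Days 0 to 42 (loss 4.5 × 42/28 = 6.75 mg). Ring B is provided on Day 42 (loss 4.5 × 14/28 = 2.25 mg). Both are returned on Day 56. If A is given B's provision date, its days are 56 − 42 + 1 = 15 and its rate is 6.75/15 × 28 = 12.6. B, given A's date, gets 2.25/57 × 28 = 1.1. One error runs upward and the other downward.

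**The outcome branch.** Ring #1 provided on Day 0, ring #2 on Day 28, outcome on Day 40, both returned later. Read literally, ring #2 is charged 40 − 0 + 1 = 41 days; from its own provision date it would be 40 − 28 + 1 = 13.

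**The case against.** The case for leaving the rule alone has several parts.

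- **Two readings of the measure.** Section 3.2 describes it as adjusting for how long the participant had the ring, which fits the operating rule. That is true, but it leaves the SAP with two definitions that give different rates in a case it foresees.
- **Frequency.** With monthly replacement and in-person visits at Weeks 2 and 4, two rings provided on Day 0 and both returned on Day 56 is not the planned course. Fields for a second ring show that the form can record one, not that it is common. This stands: the frequency is unknown.
- **Wording slips.** If the linking rule is read with provision date in place of return date, it works whenever the two provision dates differ. The outcome branch may be shorthand for both rings. Both are plausible, but neither is what the text says, and the first does not help when both rings were provided together.
- **Limited reach.** The endpoint is descriptive. Plasma dapivirine and self-report are separate ring-adherence measures, and the exposure sets in Section 3.1 rest on dispensation and discontinuation records. This stands; the primary analyses are untouched.

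A reader might also infer more than the document supports:

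- **That both rates are always halved.** This needs both rings to have been provided on the same date.
- **That fully adherent women are scored Yellow in general.** This depends on a release figure the SAP does not give; above 8.14 mg the ring stays Green.
- **That the bias is always downward.** The days error is, but a swapped link can push a rate either way, as the 12.6 above shows.

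**Conclusion.** The defect holds in a limited form. For two rings worn one after the other and returned on one date, the operating rule in Appendix III contradicts the appendix's own definition of days and counts overlapping days twice. The halving to 0.491 needs no assumption about release. It does assume the stated dates, and it affects both rings or only the first according to when the second was provided.

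The shift from Green to Yellow is conditional on a 28-day release above about 4.14 and up to 8.14 mg. That shift does not alter the ever/never exposed classification in Section 9.3, where Yellow and Green both count as exposed. The recnum link cannot be carried out as written, and the outcome branch is incomplete for ring #2.

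The text should be corrected because the SAP itself plans for this case and the remedy is cheap. How many rings are affected cannot be judged from the document.

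**What to change.** Amend Appendix III as follows.

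1. **One pooled rate.** For rings returned on one date, divide the total drug released by all of them by the calendar days from the earliest provision date to the return date, or to the pregnancy outcome date if earlier, and multiply by 28. Keep the present + 1 day convention. Enter the result once for that participant visit.
2. **Denominator.** State in Section 9.3 that the denominator for this measure is then participant visits with a valid rate, not rings.
3. **Invalid partner ring.** If one of the rings has no valid result, do not divide the other ring's loss by the pooled interval. At an assumed 4.5 mg that gives 4.5/57 × 28 = 2.2, which is the same error again. Use the remaining ring's own wear dates from the Ring Insertion and Removal CRF if they are recorded. Otherwise treat the rate as not calculable and exclude it, as Section 9.3 already provides.
4. **Linking rule.** Reword the recnum rule so that it does not refer to earlier and later return dates. With a pooled rate it is needed only to assign lot values.
5. **Outcome branch.** Apply the truncation at pregnancy outcome explicitly to both rings.

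The cost is a few lines of text and code. The pooled rate uses dates already named in Appendix III and needs no new data. The separate rates of rings returned together are given up, and an occasional visit may be lost under step 3.
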